This will be a double-blinded, randomized, placebo-controlled study to determine if botulinum toxin injection can relieve pain associated with pelvic floor spasm in women with chronic pelvic pain. We plan to study women of reproductive age with pelvic muscle spasm and pain persisting after the surgery for endometriosis. Participating women will be randomly assigned to receive either botulinum toxin or placebo (an inactive salt solution) injection. The group of women receiving placebo will serve as controls. Pregnancy tests will be assessed in women who have not had a hysterectomy at the time of botulinum toxin injection and all women will be advised not to become pregnant in the month following injection. Women will be seen again one month after the first injection to assess the effectiveness of injection. Improvement in pain after the first injection will be assessed for the primary outcome. The women will be followed for a year. All participants will be offered a single reinjection with active drug at the one month visit or later during the 1 year follow-up period if the pain returns.

The intent of this protocol is to evaluate whether botulinum toxin injection improves endometriosis-associated pain as reported by the patient and assessed by gynecology and physiatry. Patients will be seen at baseline study injection, one month after the study injection (4-7 weeks), mid-way through the study (5-8 months) and at the end of the study (11-14 months). With regards to Botulinum toxin injections, patients may receive up to 2 botulinum toxin injections (study injection of botulinum toxin or placebo and then 1 additional active botulinum toxin injection— at the one month visit or later during the year after study injection).

IV. Selection of subjects

A. Inclusion Criteria:

- Female gender
- Age between 18 and 55
- History of endometriosis at surgery
- Persistent pelvic pain for at least 3 months
- Pelvic floor spasm
- Negative pregnancy test (in women who have not had a hysterectomy)
- Willing to use reliable method of contraception for the month after botulinum toxin injection including oral contraceptives, IUD, and barrier with spermicide.
- Willing and able to give informed consent
- Willing and able to comply with study requirements

B. Exclusion criteria:

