1. A complete history including medical conditions, headaches, depression, reproductive health history regarding sexually transmitted diseases, gynecologic conditions, menstrual history, contraceptive use, current hormonal treatment for endometriosis, and pregnancy history.
2. A physical examination including a pelvic exam. The presence of pelvic muscle spasm will be assessed as part of the screening evaluation by study gynecologist.
3. Administration of standardized questionnaires to assess:
 - The presence and severity of dysmenorrhea, deep dyspareunia, and non-menstrual pelvic pain (Standardized Pelvic Pain Questionnaire). A visual analogue assessment will also be performed (Brosens,[16]) (Appendix 3)
 - The quality of life (Endometriosis Health Profile-30) will also be assessed (Jones, [17]) (Appendix 4)
 - Pelvic floor distress inventory (Barber,[29]) (Appendix 5)
 - Patient-Reported Outcomes Measurement Information System (PROMIS ®) measures of health for Anxiety, 7 item measure, Depression, 8 item measure, Fatigue, 4 item measure, Sleep Disturbance, 4 item measure [25](Appendix 6). Patient responses to the questionnaires will not be routinely reviewed during clinic visits. Therefore, we have asked the patient, to communicate directly with the study team if, at any time during her participation, she feels concerned about her mood (anxiety or depression). If a concern is identified in speaking with the patient or reviewing patient responses, the potential for additional services will be discussed.
 - Rome criteria III for Irritable Bowel Syndrome[19](Appendix 14)
 - Painful Bladder Syndrome (Parsons, [20])(Appendix 15)

- SF 36 Health Survey (Appendix 16)
 - Oswestry Disability Index (Appendix 17)
 - BPI body territories list (Appendix 18)
 - Pain Catastrophization Scale (Appendix 19)
4. Laboratory tests: CBC with differential, liver function tests, BUN, creatinine, electrolytes, sed rate, thyroid panel, ANA, Rheumatoid factor, and CPK (15 ml), Pap smear, urinalysis, urine culture, and PCR screening for gonorrhea and Chlamydia at the Clinical Center. The following laboratory tests will occur in the morning with the patient fasting: Fasting lipid panel, fasting glucose, HbA1C, CRP, am cortisol, and DHEAS. The fasting and other blood tests may be drawn on the day of other study procedures or on a separate day, at the participant's convenience.

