 5. Completing of one month's calendar of medication use and baseline pain score and baseline screening questionnaire (Appendix 1 and 2)
 6. Physiatry Assessment for central nervous system sensitization and myofascial dysfunction (Appendix 7)
 7. Patient medication guide: patients will receive the botulinum toxin a medication guide for their review (Appendix 8).

C. Injection Procedure

Eligible women agreeing to participate will be randomized to active or placebo injection. The treating gynecologist, the neurologist performing EMG monitoring, and patient will be blinded to the randomization. Injection will be performed during a clinic visit after study eligibility is confirmed. Patients will be instructed not to change any hormonal treatment of endometriosis for the one month following injection.

One hour before injection, up to 10mg of diazepam will be given orally as an anxiolytic and anesthetic cream (lidocaine 4% cream) placed on the vaginal walls. The gynecologist will perform the injection with sterile technique into areas with palpable spasm, under EMG guidance provided by a neurologist. Patients will receive either 100 U type A Botox® (onabotulinum toxin A) reconstituted with preservative-free saline or a similar volume of saline. The location and amount of toxin/saline injected will be documented using a standardized recording sheet (appendix 9). Patients will be able to leave an hour after injection but will be instructed not to drive until the effects of the sedation have worn off.

Randomization will follow a permuted block design with block sizes of 4 and 6. The Pharmacy Development Service, who will not be blinded, will assign the subject. The toxin or saline will be picked up from the pharmacy and prepared by an unblinded nurse in a private, appropriate clinic area. Syringes with the toxin in solution or saline (which are identical in appearance) will be brought to the treatment room.

On the day of botulinum toxin injections, women who have not had a hysterectomy and who are sexually active will have a urine pregnancy test to exclude pregnancy.

D. Post-injection follow-up

Subjects will be asked to complete a one month's calendar of medication use and pain score after injection.

Subjects will be contacted between 3 days and 2 weeks after injection to monitor for adverse effects including genitourinary infections and change in bowel or bladder function.

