Women who undergo a second injection at the 1 month visit or at any time later within the 1 year follow-up period with the same pretreatment medication, precautions, injection technique, and follow-up as with the first injection. If this injection occurs outside of a scheduled visit, a new baseline will be established to include completion of Standardized Pelvic Pain questionnaire, standardized endometriosis QOL questionnaire, Rome criteria III for Irritable Bowel Syndrome, Painful Bladder Syndrome and PROMIS HRQL measures of sleep, fatigue, anxiety and depression, BPI body territories list, SF 36 Health Survey, Oswestry Disability Score and pain catastrophization scale. All subjects will receive botulinum toxin if a second injection is needed regardless of the randomization group. On the day of botulinum toxin injections, women who have not had a hysterectomy and who are sexually active will have a urine pregnancy test to exclude pregnancy. Women will be asked if they have had urinary or fecal incontinence or pelvic organ prolapse. Those experiencing these symptoms will be systematically assessed and, if significant, will not have an injection. Hormonal treatments and pain medications will be reviewed. One month later, several questionnaires will be completed including: Standardized Pelvic Pain questionnaire, standardized endometriosis QOL questionnaire, Rome criteria III for Irritable Bowel Syndrome, Painful Bladder Syndrome and PROMIS HRQL measures of sleep, fatigue, anxiety and depression BPI body territories list, SF 36 Health Survey, Oswestry Disability Score and pain catastrophization scale. Patients may come for an optional study visit at the one month time point.

Although only the results of the randomized injection will be used for statistical analyses, descriptive data on pain relief will be collected on the outcome of the second injection using the one month calendar of pain and medication use, and botulinum toxin patient response inventory.

F. Mid- and End-Study follow-up

Although only the results of the randomized injection will be used for statistical analyses, descriptive data on pain relief will be collected on the outcome of the additional injection using the one month calendar of pain and medication use, and the botulinum toxin patient response inventory. Additionally, at the mid-way (5-8 months) and study end (11-14 months) study visit,

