blood pressure will be checked and a pelvic exam will be done. At the mid-way (5-8 months) and study end (11-14 months) follow-up, the following laboratory tests will occur in the morning with the patient fasting: Fasting lipid panel, fasting glucose, HbA1C, CRP, am cortisol, and DHEAS. The standardized Pelvic Pain Questionnaire and standardized endometriosis-related QOL questionnaire, Rome criteria III for Irritable Bowel Syndrome, Painful Bladder Syndrome and PROMIS HRQL measures of sleep, fatigue, anxiety and depression, BPI body territories list, SF 36 Health Survey, Oswestry Disability Score, and pain catastrophization scale will be assessed. Patient responses to the questionnaires will not be routinely reviewed during clinic visits. Therefore, we have asked the patient, to communicate directly with the study team if, at any time during her participation, she feels concerned about her mood (anxiety or depression). If a concern is identified in speaking with the patient or reviewing patient responses, the potential for additional services will be discussed.

Women who become pregnant after the study injection and one month study visit for the primary outcome assessment and remain in the study (per section B.3 below) may have an additional study assessment beyond the month 12 visit, if needed, to permit a return to baseline status after the immediate post-partum period. The assessment will include completion of study questionnaires and rating scales. An in-person examination and research blood tests (as per the 12 month visit) may also be done, if feasible. These participants may also be offered a 2nd study injection up to one year after delivery or other pregnancy outcome, if they did not have a 2nd injection earlier in the study. Procedures for the later 2nd injection will be per Section E “Second Injection” procedures (above), including data collection, a new baseline assessment, injection procedure and one month assessment.

G. Psychiatry assessment for central nervous system sensitization and myofascial dysfunction

At the study end (11-14 months), women will be assessed by the psychiatrist for signs of central nervous system sensitization and myofascial dysfunction, and will be assessed by the gynecology team.

H. Medications

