The risk of botulinum toxin usage during pregnancy is not known. The literature reports several women who received botulinum toxin injections while pregnant without adverse effects on either the mother or fetus. It is not known if toxin injected into a nursing mother could adversely affect the infant. Although women who are pregnant or are nursing are excluded from receiving botulinum toxin in this protocol, we will inform subjects of the unknown risk. Women who become pregnant after the study injection of botulinum toxin or placebo and after the one month study visit needed to assess the primary outcome may continue in the protocol. Pregnant participants may undergo all study outcome assessments but will not be eligible for a 2nd, optional botulinum toxin injection.

The participation of pregnant women in the study under these conditions meets the 45CFR46 subpart B criteria for research with pregnant women as follows:

§46.204 Research involving pregnant women or fetuses.

Pregnant women or fetuses may be involved in research if all of the following conditions are met:

- (a) *Where scientifically appropriate, preclinical studies, including studies on pregnant animals, and clinical studies, including studies on nonpregnant women, have been conducted and provide data for assessing potential risks to pregnant women and fetuses;*

The research procedures that will be performed in pregnant women include physical examination, phlebotomy with blood volume limited to 10 ml and completion of computer and pen-and-pencil scales and questionnaires. These procedures do not pose risk to pregnant women or fetuses.

- (b) *The risk to the fetus is caused solely by interventions or procedures that hold out the prospect of direct benefit for the woman or the fetus; or, if there is no such prospect of benefit, the risk to the fetus is not greater than minimal and the purpose of the research is the development of important biomedical knowledge which cannot be obtained by any other means;*

The risks to the fetus from study interventions are not greater than minimal. The purpose of the research is the development of important biomedical knowledge on changes in chronic pelvic pain and response to prior botulinum toxin injection during pregnancy which cannot be obtain by other means.

- (c) *Any risk is the least possible for achieving the objectives of the research;*

The risk is the least possible for achieving study objectives. The risk assessment is minimal risk.

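### Sections III and IV.A require a pregnancy test in every woman without a hysterectomy, but the procedures in V.C and V.E schedule it only for those who are also sexually active

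*Combined protocol and SAP*

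**What the plan says.** Two parts of the protocol set the rule without reference to sexual activity. Section III (Study Design and Methods) says: "Pregnancy tests will be assessed in women who have not had a hysterectomy at the time of botulinum toxin injection". IV.A (Inclusion Criteria) lists: "Negative pregnancy test (in women who have not had a hysterectomy"). IV.A does not say on which day the test is to be done.

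The procedures say something narrower. V.C (Injection Procedure) provides that on the day of injection "women who have not had a hysterectomy and who are sexually active will have a urine pregnancy test to exclude pregnancy", and V.E (Second injection) repeats the sentence. The laboratory item in V.B (Pre-injection medical evaluation) lists blood tests and "Pap smear, urinalysis, urine culture, and PCR screening for gonorrhea and Chlamydia at the Clinical Center", but no pregnancy test.

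Three further statements bear on the point:

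- V.C: "Injection will be performed during a clinic visit after study eligibility is confirmed".
- V.E: "All subjects will receive botulinum toxin if a second injection is needed regardless of the randomization group".
- V.F, on the second injection offered after a pregnancy during the study: "Procedures for the later 2nd injection will be per Section E".

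**The concern.** A woman without a hysterectomy who reports that she is not sexually active must have a negative test to enter, yet no step in Section V tells staff to do one. If they follow V.B and V.C literally, she is injected with an entry criterion unconfirmed. At the second injection, V.E omits a test that section III calls for.

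What is at stake is safety and the documentation of eligibility. IX.B says: "The risk of botulinum toxin usage during pregnancy is not known". Pregnancy is an exclusion under IV.B, and IX.B bars pregnant participants from the second injection. That injection is active drug for everyone and can be given at any time in the one-year follow-up, or up to one year after a pregnancy outcome, so a test at entry could not cover it. The contraception criterion in IV.A concerns the month after injection and does not rule out a pregnancy that already exists.

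**Working it through.** The plan gives no figure to reproduce. The check is to set every provision on pregnancy testing side by side.

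| Place | Who is tested | When |
|---|---|---|
| III | All women without a hysterectomy | At injection |
| IV.A | All women without a hysterectomy | For entry; day not stated |
| V.A Screening | No test listed | – |
| V.B Pre-injection evaluation | No test listed | – |
| V.C First injection | No hysterectomy **and** sexually active | Day of injection |
| V.D Post-injection follow-up | No test listed | – |
| V.E Second injection | No hysterectomy **and** sexually active | Day of injection |
| V.F Mid- and end-study follow-up | No test listed; later second injection refers back to V.E | – |

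**First injection.** Take a woman without a hysterectomy who is recorded as not sexually active. Scheduled tests before her first injection: V.A 0 + V.B 0 + V.C 0 = 0. IV.A requires a negative result. V.C does not waive that, because injection must wait for confirmed eligibility, but no procedure produces the result.

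**Second injection.** Scheduled tests: V.E 0. IV.A is an entry criterion and does not govern here, so the conflict is with section III alone. Because V.F refers back to V.E, the same gap applies to a second injection given after a pregnancy.

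**Size.** Section III allows up to 2 injections per woman, so an affected woman may have up to 2 injections without a scheduled test. Reaching 2 assumes that she remains not sexually active and accepts the optional second injection. VII.B plans for 30 randomized women. Testing everyone at both injections would need at most 30 × 2 = 60 urine tests. That is a ceiling on all testing and does not measure the gap. The added tests are only those for women without a hysterectomy who are not sexually active. The document gives neither the share with a hysterectomy nor the share not sexually active, so that number cannot be computed.

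**The case against.** The strongest reply is that the first injection is already controlled. IV.A binds every woman without a hysterectomy, the note under IV.B calls for negative results to be documented, and V.C allows injection only once eligibility is confirmed. The V.C test can then be read as a same-day repeat for women who could have conceived since entry. On this reading the only first-injection defect is a missing line in V.B. That would indeed be a smaller fault, but the line is missing, so the entry test is required and never scheduled. The documentation note is also tied by its asterisks to other criteria and goes on to discuss cervical and infection screening.

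For the second injection, one can say that a specific procedure outranks a one-sentence overview, and that the identical wording in V.C and V.E suggests a deliberate rule. Other safeguards exist: V.E applies the same precautions as at the first injection, V.D includes a gynecological examination at the one-month visit, and pregnant participants are ineligible. These reduce the remaining risk but do not replace a test. For a second injection outside a scheduled visit, the new baseline in V.E consists of questionnaires, and no gynecological examination is listed.

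It is also fair to say that the women left untested are the least likely to be pregnant, and that about half of them receive saline first. Both points stand and limit the weight of the concern. They leave the safeguard resting on a report of sexual activity that the supplied text does not define or tie to a time window.

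**Conclusion.** The concern holds. The protocol contradicts itself on who is tested for pregnancy. For a woman without a hysterectomy who is recorded as not sexually active, Section V schedules no test before either injection, although IV.A requires one at entry and section III at each injection.

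The practical weight is low. The number affected is unknown, the women concerned are unlikely to be pregnant, and a history and pelvic examination precede the first injection. The sample size and the primary analysis are untouched. The change should still be made, because the risk in pregnancy is unknown, the second injection is always active, and the correction costs almost nothing.

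The conclusion rests on the protocol text alone. The contents of the appendices were not available, and a form there may prompt for the test.

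**What to change.** Delete the five-word sexual-activity condition from the pregnancy-test sentence in both V.C and V.E. Every woman without a hysterectomy then has a urine test on the day of each injection. This satisfies section III and IV.A, and it covers the later second injection in V.F through its reference to V.E.

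Two alternatives are weaker. Adding a pregnancy test to the laboratory list in V.B would settle entry, but it would leave V.E in conflict with section III. Narrowing III and IV.A to match V.C and V.E would remove the contradiction, but in the less safe direction.

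The cost is a wording change in two places and at most two extra urine tests per affected woman. Randomization, blinding and the analysis do not change.

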- Women with other causes of chronic pelvic pain including infectious, gastrointestinal, psychological disorders, fibromyalgia and chronic fatigue syndrome based on review of medical history within 1 year of first study visit
- untreated severe cervical dysplasia or other gynecologic condition*
- clinically significant abnormalities on physical or laboratory examinations that require evaluation or treatment or that would make participation unsafe.*
- Hysterectomy and bilateral salpingo-oophorectomy
- Pregnancy
- Lactation
- Allergy to albumen or botulinum toxin
- Presence of antibodies to botulinum toxin or loss of response to previous injections for any indication
- A known neuromuscular junction disorder such as myasthenia gravis or Eaton-Lambert syndrome
- History of urinary or fecal incontinence
- Known pelvic prolapse

**Eligibility will be based on a physical exam at NIH at the first study visit, as well as history and available medical records within 1 year before the study visit. Negative test results will be documented to confirm study eligibility. If the Pap and the GC and chlamydia tests were not done outside of the NIH within the previous year, or if documentation of the negative test results is not available, we will await the results of the screening tests done at the NIH before administering the study medication.*

C. Criteria for withdrawal of subjects from the study

- Inability to perform home monitoring or comply with study visit schedule
- Occurrence of an adverse event that precludes further participation in the study at the discretion of the investigator
- Subject wishes to terminate participation

- Incontinence of urine or feces, or pelvic organ prolapse occurring after injection

D. Study discontinuation

- If more than 2 subjects develop incontinence or pelvic prolapse, the study will be discontinued.

V. Study procedures

A. Screening process: Women with at least a three-month history of pelvic pain suggestive of endometriosis and who have a surgical diagnosis of endometriosis will be considered for this study. Eligible women will complete written consent via telephone interview and will complete a baseline screening questionnaire (appendix 1), one month calendar (appendix 2), and submit records confirming surgical diagnosis.

B. Pre-injection medical evaluation:

This will occur in an outpatient area at the Clinical Center and will include the following for all patients:

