They will be offered a botulinum toxin injection at 1 month after the first injection, and will return for follow-up clinic visit scheduled at that time. At that visit, the prior month's pain symptoms and use of hormonal treatments and pain medications will be reviewed, and a gynecological examination performed. At the one month visit, several questionnaires will be completed, including: Botulinum toxin patient response inventory (Appendix 10), Standardized Pelvic Pain questionnaire, standardized endometriosis QOL questionnaire, Rome criteria III for Irritable Bowel Syndrome, Painful Bladder Syndrome and PROMIS HRQL measures of sleep, fatigue, anxiety and depression, BPI body territories list, SF 36 Health Survey, Oswestry Disability Score, and pain catastrophization scale. For those opting for a second injection, this will be done as described below.

After the 1-month visit, the patient will be contacted every three months for up to 1 year, to determine how long any effects may have lasted.

E. Second injection

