Other side effects of botulinum toxin include a flu-like syndrome characterized by myalgias and malaise in the week following injection, especially in patients receiving higher doses than planned here. The symptoms respond well to acetaminophen. There has been a single case report of fatal anaphylaxis in a patient who received botulinum toxin diluted with lidocaine [34]. We will not be preparing the botulinum toxin with lidocaine. Such a severe reaction is highly unlikely.

The FDA requires that all forms of botulinum toxin carry a “black box” warning. In rare cases, botulinum toxin can cause symptoms suggestive of botulism. The symptoms include severe weakness, hoarseness or trouble talking, loss of bladder control, difficulty breathing, trouble swallowing, double vision or blurred vision and drooping eyelids. These symptoms have occurred mainly in children with cerebral palsy who received high doses of botulinum toxin. They can also occur, however, in adults receiving botulinum toxin. Allergan, the company who manufactures the toxin we will be using in this study, has recently developed a patient information pamphlet that we will be handing out to patients as part of the study (Appendix 9).

Offering injection with botulinum toxin at one month is critical to the study design and significantly enhances study enrollment and continuation. The need for the one-month repeat injection is considered a study outcome measure.

There is no safety concern with dose to be used. 100 Units is used at each injection. Those electing the one-month injection, who were randomized to toxin with the first injection, will receive a total of 200 U. The safety of toxin injection with a cumulative dose of 200 U is well established. Many patients receive a dose of 200 U or more at a single injection session. In addition, women with incontinence are excluded from participating.

Neutralizing antibodies to botulinum toxin type A can develop and are more likely in patients receiving high doses or frequent injections. The formation of antibodies is associated with loss of response to further injections with that toxin type. With the one-month interval, at least half of those requesting reinjection will have received placebo. For those receiving toxin with the first injection, the likelihood of antibody formation is exceedingly low as the one-month interval between injections is only used a single time. All other injections are spaced at least 3 months apart.

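### After the early contact, the only explicit incontinence and prolapse question is tied to opting for re-injection, although a third case stops the study

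*Combined protocol and SAP*

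**What the plan says.** Two rules depend on these events. Section IV.C lists as a withdrawal criterion: "Incontinence of urine or feces, or pelvic organ prolapse occurring after injection". Section IV.D adds: "If more than 2 subjects develop incontinence or pelvic prolapse, the study will be discontinued".

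The follow-up text provides the following:

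- **Early contact, all women (V.D):** "between 3 days and 2 weeks after injection to monitor for adverse effects including genitourinary infections and change in bowel or bladder function". Prolapse is not named.
- **One-month visit, all women (V.D; 4-7 weeks by Section III):** "pain symptoms and use of hormonal treatments and pain medications will be reviewed, and a gynecological examination performed". Questionnaires are also completed, including the botulinum toxin patient response inventory (Appendix 10).
- **Three-monthly contacts (V.D):** "the patient will be contacted every three months for up to 1 year, to determine how long any effects may have lasted".
- **Second injection, only for women who opt for it (V.E):** "Women will be asked if they have had urinary or fecal incontinence or pelvic organ prolapse". Women with symptoms are assessed and, if the symptoms are significant, are not injected. Follow-up is as for the first injection. One month later questionnaires are completed, and a visit at that point is optional.
- **Mid- and end-study visits (V.F):** blood pressure, pelvic examination, laboratory tests and questionnaires.

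The pre-injection list (V.B.3) includes "Pelvic floor distress inventory (Barber,[29]) (Appendix 5"), but no follow-up list does. Section VII.B plans to tabulate side effects and weakness and to compare them by Fisher's exact test.

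**The concern.** The discontinuation rule is a count with a low threshold: the third affected woman meets it. If exactly three women are affected, one missed case leaves it unmet. Such a count is best fed by a question put to everyone on the same schedule. Here the explicit question at one month is put only to women who choose re-injection, and need for re-injection at one month is itself a secondary outcome (VII.A).

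That choice is likely to differ by arm. On the one-month interval, Section IX.B.3 expects that "at least half of those requesting reinjection will have received placebo". The women who are asked would then be at least as often placebo-treated as toxin-treated, whereas incontinence is a named risk of the toxin.

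The V.E question also comes before the second injection, and only one re-injection is allowed. A re-injected woman is therefore not explicitly asked it again afterwards, although that injection is always active toxin.

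**Working it through.** The protocol states no expected event rate and no operating characteristic for the rule, so there is no figure to reproduce. The main check is textual: of the follow-up steps listed above, only the early contact and the V.E screen name bowel, bladder or prolapse symptoms as something to ask about. Three short calculations bound what follows from this.

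**1. Interval in which a transient episode could pass unasked.** Inputs: early contact on day 3 to 14 (V.D); one-month visit on day 28 to 49 (4-7 weeks, Section III); an episode of 21 days, since IX.B.3 says incontinence would resolve over 3 weeks. The number of onset days for an episode lying wholly between contact and visit is max(0, visit day − 21 − contact day).

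| Contact day | Visit day | Gap (days) | Onset days |
|---|---|---|---|
| 3 | 28 | 25 | 4 |
| 3 | 49 | 46 | 25 |
| 14 | 28 | 14 | 0 |
| 14 | 49 | 35 | 14 |

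The range is 0 to 25 days. V.E gives no window for the questionnaires one month after a second injection. If they are completed on day 28 the range is 0 to 4 days; if the 4-7-week window applies it is again 0 to 25.

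**2. Who would be asked at one month (illustration).** Inputs: 30 randomized, taken as 15 per arm; 70% and 20% improving (VII.B). Assume that all non-improvers and a fraction f of improvers opt in. The share asked is 0.3 + 0.7f on toxin and 0.8 + 0.2f on placebo.

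- f = 0: 15 × 0.30 = 4.5 toxin and 15 × 0.80 = 12 placebo; placebo share 0.80/1.10 = 73%.
- f = 0.5: 15 × 0.65 = 9.75 and 15 × 0.90 = 13.5; placebo share 0.90/1.55 = 58%.
- f = 1: 15 and 15; placebo share 50%.

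This agrees with the protocol's own expectation of at least half. It describes who is asked, not whose events are detected.

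**3. Effect on the planned Fisher comparison.** Two-sided p at 15 per arm:

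- 3 vs 0 events: 0.22
- 4 vs 0 events: 0.10
- 5 vs 0 events: 0.042

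Even with every event in one arm, significance needs five, which is more than the three that meet the discontinuation rule.

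**Sensitivity of the rule to missed cases (assumed rates only).** With X ~ Binomial(30, q × s), where q is the true event rate and s the share detected, P(X ≥ 3) at q = 5% is 0.19, 0.10 and 0.04 for s = 100%, 75% and 50%. At q = 10% it is 0.59, 0.39 and 0.19. Neither q nor s can be read from the documents. These values show that the rule would respond to missed cases, not that cases are missed.

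**The case against.** The strongest reply is that the V.E sentence was never the trial's means of detection; it is a check before a further injection. Detection for all women rests on other provisions:

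- All adverse events within 6 weeks of injection are tracked whatever their cause, and later ones are reported if related (VIII).
- Visit questionnaires are said to cover side effects (IX.B.1), and weakness is among the planned variables (VII.B).
- Appendix 10 goes to every woman at one month.
- Pelvic examinations can find prolapse.
- Women receive a medication guide (V.B.7), and questionnaire data are reviewed for completeness within 48 hours of a visit (XVIII.2).

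The appendices are listed by title only and the DSMB Charter is separate, so an existing item may already ask the question.

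Most of this stands. A reader might infer that safety monitoring stops after two weeks; the provisions above show that it does not. A reader might also infer that the side-effect comparison between arms is biased in a way that matters; at these numbers the Fisher test is hardly affected. V.F says that questionnaire responses are not routinely reviewed at visits, which might suggest that such answers go unread. That remark concerns mood, and XVIII.2 provides a data review.

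The objection is also right about late follow-up. Excess weakness usually improves within 1-2 months (IX.B.3), so asking at mid- and end-study adds little for women who are not re-injected. Nor should solicited answers go straight into the discontinuation count: without the V.E assessment step and Section VIII's relatedness distinction, mild or unrelated leakage could change how the rule operates.

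What remains is that none of these provisions states a targeted question for every woman after the early contact. An examination is unlikely to reveal incontinence that has already resolved.

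**Conclusion.** The point holds in a limited form. In the text shown, whether a woman is explicitly asked about incontinence or prolapse at one month depends on a choice made after randomization, although these events feed a rule that can end the study. The main exposure is transient incontinence that begins after the early contact and resolves before the 4-7-week visit, together with the corresponding interval after the second injection.

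Any under-count is plausible, not demonstrated. Its size is unknown and may be negligible, since IX.B.3 calls sphincter weakness very unlikely at the planned dose. It also narrows for women re-injected later in the year, because the V.E question looks back. The documents do not support the stronger claim that the discontinuation rule cannot work.

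The conclusion assumes that no unshown form already asks every woman this question; if one does, only a cross-reference is missing. It is a minor point with a cheap remedy.

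**What to change.** In V.D, ask every woman the existing V.E question at the one-month visit, before the re-injection decision, worded to cover the time since her last study contact. In V.E, ask it again with the questionnaires completed one month after any second injection, whether or not she attends the optional visit. Use the one-month answers for the between-arm side-effect table.

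Send positive answers through the assessment already described in V.E and the adverse event process in Section VIII. Leave the discontinuation rule, and what counts toward it, unchanged. Asking at the three-monthly, mid- and end-study contacts is optional. If Appendix 10 or another form already contains the question, name it in V.D and V.E as the source instead.

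The cost is a few minutes per woman and possibly more mild episodes reported.
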